### **m. Intention- To -Treat (ITT)**

The intention to treat population consists of all patients randomized. The primary and secondary endpoints of patients randomized to early goal-directed decrement of preload and afterload (intervention group) will be compared to the patients randomized to standard of care by the intention-to-treat principle.

Patients without a follow-up assessment at 6 months for the primary endpoint will be censored at the time of the last follow-up information available.

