### **n. Per-protocol (PP)**

The per-protocol population PP consists of all patients randomized, who received at least one dose of the study drug (Hydralazine and/or nitrates in the form of capsules, spray and/or transdermal application) and had a baseline plus follow-up assessment (180 days) of the primary endpoint completing the study without major protocol deviations. PP analyses are planned as part of sensitivity analyses.

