### **p. Safety population**

For the analysis of safety, including protocol pre-defined adverse events, all randomized patients will be included in the safety population if they received at least one dose of the randomized study drug, and had at least one subsequent safety-related visit.

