## 11. Evaluation of safety parameters

### ff. Adverse events

Specific adverse events (AE) will be documented and investigated only during the course of

	Intervention arm (N=)	Standard of care arm (N=)
--	--------------------------	------------------------------

---

the index hospitalization (see “11.1.1.Brief summary of adverse events”). Additionally, during the first 180 days, all serious adverse events (SAEs) as defined by current Good Clinical Practice standards will be collected, fully investigated and documented in source documents and case report forms (CRF). Study duration encompasses the time from when the participant signs the informed consent until the last protocol-specific procedure has been completed (last FU at 360 days).

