**Supplemental Table 1. Events in all Patients**

Data expressed as nr of patients with event (% of patients) and total nr of event reported.

\*defined as Systolic arterial pressure < 80 mmHg over 30 minutes

Supplemental Table 1. Events in all Patients

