### **iii. Analysis of adverse events**

Intention- To -Treat (ITT): adverse events will be reported as rates: total nr of events per patient and compared intervention arm vs standard of care arm using Chi square test with two-sided p-values.

Safety population are the patients who received at least once the study drugs (hydralazine and/or nitrates in the form of capsules, spray and/or transdermal application), and events are reported up to last confirmed intake of the study drug.

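### The safety and per-protocol populations require receipt of hydralazine or nitrates, so their control side is a physician-selected subset, and the safety event window can close before up-titration ends

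*Combined protocol and SAP*

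**What the plan says.** The SAP describes the safety population twice. Section 5.6 (heading p) assigns the analysis of safety, including the predefined adverse events, to randomised patients "if they received at least one dose of the randomized study drug, and had at least one subsequent safety-related visit". It sets no event window. Section 11.1.3 (heading iii, Analysis of adverse events) says: "Safety population are the patients who received at least once the study drugs (hydralazine and/or nitrates in the form of capsules, spray and/or transdermal application". It drops the visit condition and adds a window: "events are reported up to last confirmed intake of the study drug".

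The per-protocol population in section 5.4 (heading n) is likewise restricted to patients "who received at least one dose of the study drug (Hydralazine and/or nitrates in the form of capsules, spray and/or transdermal application", with further conditions.

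Section 11.1.3 opens with a different analysis, by intention to treat, in which "adverse events will be reported as rates: total nr of events per patient and compared intervention arm vs standard of care arm". For that set, "The intention to treat population consists of all patients randomized". The display is titled "Supplemental Table 1. Events in all Patients", although section 11.1.2 makes its production conditional on applicability and request. Under section 11.1, specific adverse events "will be documented and investigated only during the course of" the index hospitalisation, and serious adverse events are collected for 180 days.

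In the protocol, the Study Therapy Control Group text and Figure 5b allow controls a transdermal nitrate at 0 to 10 mg per 12 h. Higher-dose nitrates or hydralazine are strongly discouraged, and hydralazine has no place in the control schedule. In the intervention arm hydralazine stops at 48 h, while ACE-inhibitor/ARB up-titration starts on day 2 and runs to day 7 (Figure 5a and the text around it).

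**The concern.** Hydralazine and high-dose nitrates are what distinguish the intervention arm. If receiving them, or any nitrate, is the ticket into an analysis set, nearly all intervention patients enter. A control enters only when a physician decided after randomisation to give a nitrate. That decision probably depends on blood pressure and severity, which also drive hypotension, renal events and outcome, so randomisation no longer protects the comparison. The per-protocol efficacy sensitivity analysis has the same weakness.

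The window is a second problem. Rapid ACE-inhibitor/ARB up-titration is part of the strategy under test, yet it is not among the drugs that define last intake. Creatinine increase, hyperkalaemia and hypotension are listed adverse events, and they can occur while those doses are still rising.

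The trial's hypothesis includes that the strategy is safe. If the safety-population report became the basis for that statement, it would rest on a non-randomised contrast observed for different lengths of time in the two arms.

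**Working it through.** No stated figure has to be reproduced. The check compares definitions and counts days.

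**1. Who enters the control side of the safety set?** Inputs: 385 patients per arm (SAP section 3.2) and the share q of controls given any nitrate. The documents do not give q, so it is an assumption. Controls in the set = q × 385:

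| q (assumed) | Controls in set | Intervention patients (if all dosed) |
|---|---|---|
| 0% | 0 | 385 |
| 10% | 38 | 385 |
| 25% | 96 | 385 |
| 50% | 192 | 385 |
| 100% | 385 | 385 |

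Figure 5b permits a nitrate for every control and requires it for none, so the full range is possible. If the randomised study drug in section 5.6 is read strictly as something only the intervention arm is randomised to, the control set is empty whatever q is.

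Selection bias is the main issue, but precision suffers too. As an illustration, take assumed event rates of 10% and 5%, a two-sided 5% level, and power = Φ((0.05 − 1.96 × SE₀)/SE₁), with SE₀ pooled and SE₁ unpooled. For 385 vs 96, SE₀ = 0.0327 and SE₁ = 0.0270, giving 30%. The same formula gives 11% for 385 vs 38, 54% for 385 vs 192, and 75% for 385 vs 385.

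**2. When does the window close?** Up-titration covers days 2 to 7, which is 6 days. Hydralazine ends at 48 h, so the last patch sets the last intake. If L is the last patch day, the up-titration days left outside number 7 − L, for a patient still in hospital on day 7:

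| Source for patch duration | L | Days outside |
|---|---|---|
| Figure 5a, systolic 90–130 mm Hg (day 5 cells blank) | 4 | 3 of 6 (50%) |
| SAP section 8.2.3 (5 days); also Figure 5a above 130 mm Hg | 5 | 2 of 6 (33%) |
| Protocol text after Figure 5a (taper until discharge) | discharge | 0 of 6 |

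These statements disagree and must be reconciled. Blank cells may also be an effect of text extraction.

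Doses are still rising in the affected days: at 90–110 mm Hg, Figure 5a lists ramipril 3.75–5 mg/d on day 4 and 10 mg/d on day 7. The cut-off has no lag, while creatinine and electrolytes are measured every 24 to 72 hours in the first week (protocol, General Procedure for Both Groups), so a rise that began inside the window may be detected after it closes.

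**3. Is the window the same in both arms?** No. Control nitrates have no scheduled end before discharge (Figure 5b; Duration of Treatment with Study-Specific Medication), so a nitrate-treated control may be observed for longer than an intervention patient. A control without nitrates has no last intake and hence no window.

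**4. Which analysis is the main one?** Section 5.6 points to the safety population. Section 11.1.3 gives a between-arm test only for intention to treat. Nothing ranks them.

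**The case against.** The strongest reply is that the SAP already contains a sound safety comparison. The intention-to-treat analysis in section 11.1.3 covers all randomised patients, has no on-drug cut-off and is the only one there with a stated test. Several harms are also secondary endpoints compared by intention to treat: symptomatic hypotension, acute coronary syndrome and ICU admission in the index stay, creatinine at 48 h and discharge, and 180-day mortality. The safety-population sentence says only that events are reported, and the per-protocol set serves sensitivity analyses alone.

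Most of this stands, and it rules out some stronger readings:

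- A reader might infer that the trial has no valid control group for safety, or that late up-titration harms are counted nowhere. The documents do not support that: the intention-to-treat comparison counts them while the patient is in hospital.
- A reader might infer from the visit condition in section 5.6 that day-1 deaths drop out, because active adverse-event search starts on day 2. That is not supported: a safety-related visit is undefined, and section 11.3.1 schedules examinations from 30 minutes onward.
- A reader might count three of seven days as lost. Up-titration begins on day 2, so the denominator is six, and three is only one of several readings. SAP section 8.2.2 adds another, with exposure of six days or until discharge.

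The reply does not resolve the conflict between sections 5.6 and 11.1.3, name a main analysis, or make the all-patient table certain. Hyperkalaemia is not a secondary endpoint, so its comparison depends wholly on the adverse-event analysis. Reading section 5.6 generously, as any assigned treatment, would admit controls, but section 11.1.3 closes that route by listing the drugs.

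**Conclusion.** The concern holds for the safety and per-protocol populations as defined. Their control side is a subset selected by physicians after randomisation, of unknown size between 0 and 385, and empty on a strict reading of section 5.6. The safety-population window leaves 3, 2 or 0 of the 6 up-titration days outside, depending on which patch schedule applies and assuming a stay through day 7.

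The defect does not extend to the intention-to-treat adverse-event comparison, which is valid in its population and counts in-hospital harms. What is missing is a statement that this comparison is the main safety analysis. As written, the SAP assigns safety to the weaker set, defines that set in two ways, and leaves the all-patient table optional. The power figures are illustrations under assumed event rates; the conclusion does not depend on them.

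**What to change.** In SAP sections 5.4, 5.6 and 11.1.1 to 11.1.3:

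1. Name as the main safety analysis all randomised patients by assigned arm, with one window common to both arms: the index hospitalisation for adverse events and 180 days for serious adverse events.
2. Use one definition of the safety population in sections 5.6 and 11.1.3.
3. Produce the all-patient event table unconditionally.
4. Delete the on-drug cut-off, or keep it as a supplementary description of the intervention arm only.
5. Define per-protocol by adherence to the assigned strategy in each arm, not by receipt of hydralazine or nitrates.
6. Reconcile the statements on patch duration in Figure 5a, the protocol text that follows it, and SAP sections 8.2.2 and 8.2.3.

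The cost is SAP wording and table shells, plus the reconciliation of the patch passages. No new data are needed for the safety analysis: adverse events and serious adverse events are already collected in both arms over these periods.

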### **iv. Listing of adverse events by patient**

Listing of adverse events per patient are provided on request.

### **gg. Concomitant medications**

Concomitant medications are reported inside the medication tables. No important interactions are to be noted.

### **hh. Vital signs and physical examination**

#### **i. Findings in vital signs and physical examinations**

Clinical examinations are conducted at baseline and again at 30min, 1, 2, 4, 6, 12, 18 hours, as well as at 2-6 days one time measurement during the index hospitalization. Assessment will include heart rate, oxygen saturation, blood pressures, breathing rates and weight. Dyspnea assessment are planned at baseline and at 24 hours and/or day six or discharge (whichever comes first). Edema assessment are planned at baseline and/or day six or discharge.

#### **ii. Other safety evaluations**

##### **11.1.1. Other observations related to safety**

No other safety observations, assessments or analyses are currently defined and planned for this statistical analysis plan.
